The investigators recognize that this intervention may lead to attrition. To reduce the risk of participant drop-out, participants will be reminded of sessions with a phone call, e-mail, and Amulet messaging reminder from the RA. Individuals will be compensated with sandwiches/snacks plus \$25 gift card for the focus groups of the qualitative aim (Aim 1a), \$25 gift card for the subject semi-structured interviews, a nominal \$10/hour payment for the prevalidation phase of Aim 1b (cash, gift-card), a \$25 gas card each for Aim 1b, \$100 for completing >80% of the visits and assessments for the three-month program (Aim 2) - \$25 per assessment, and \$200 for completing >80% of the visits and assessments at 6-months (Aim 3). Payment will be made at study conclusion according to institutional policies. They will also receive a fixed schedule of items (pens, notepads, thank you cards) to recognize their participation to date. Participants will have the option of declining such incentives at any time. We will provide a \$25 gas card or equivalent for each visit (Aim 4).

No involvement of special vulnerable population such as fetuses, neonates, pregnant woman, children, prisoners, institutionalized individuals or others who may be considered vulnerable will be included in this study. The study will be a single-arm study and there will be no assignment to a study group for this study.

Retention

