We recognize that attrition rates in obesity studies range between 25-50%. For Aim 1a (qualitative studies), we will target 4 focus groups of 6-8 individuals (24-32 individuals total), 6-8 individual semi-structured interviews, 6 primary care clinicians, and 4 community leaders for a maximum total of 50 individuals. For Aim 1b, we anticipate recruiting 75 individuals for a target of 60 individuals. Conservative estimates suggest that 14 individuals need to be recruited to allow for 16 individuals for Aim 2 at study conclusion. For Aim 3, our target is 40 individuals. We anticipate recruiting 53 individuals. We believe that these targets are feasible with our local population. We anticipate recruiting individuals in one wave for Aim 1, two waves for Aim 2, and in 4 waves for Aim 3 to reach target enrollment and completion. Should we exceed target enrollment and completion, we will continue gathering measurements on all individuals. With the new arm (MOWI-P), we anticipate recruiting an additional 16 subjects. For Aim 4 (Weight Maintenance), we anticipate recruiting 60% of each of the original sample for Aim 2 (ie: 4 waves @ 8 = $32 \times 0.6 =$ approximately 19 subjects).

STATISTICAL DESIGN AND POWER

Aim 1 (Qualitative assessment) will use mixed-methods to adapt Amulet and MOWI for use in rural older obese adults.

Aim 1b (Adapt Amulet): Adapt Amulet to assess functional measures: Agreement/reliability for upper/lower strength (Thera-bands and STS), gait speed, and steps will be calculated. Descriptive statistics will outline distributions, mean differences/ ratios assessing Amulet's measures to corresponding steps, speed or strength, and for usability testing. Relative/absolute test-retest reliability of mean differences between test/retest using 95% confidence intervals and standard error of mean to examine bias and intra-class coefficients will be reported. Paired t-test will test for bias. Scatterplots and Bland-Altman plots for miscalibration will be viewed, and a relation of variance to mean (data heteroscedasticity) to assess agreement between measures.

Data and Safety Monitoring Plan

Per the instructions for the “Human Subjects” section of PHS-398/SF424 (R+R) the proposed study intervention could have harmful effects but does NOT meet the criteria for an NIH-defined Phase III trial.

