The current intervention is not an experimental agent and its proposed risk to individuals is likely considered low. We anticipate that there will be a low risk of adverse medical events associated with this intervention. A physician will be available on the premises during all intervention sessions and monitor patient progress and/or adverse events during each session and be responsible for monitoring the data and safety for this proposal. However, we intend on establishing an independent data safety monitoring process that will include an independent data safety monitoring board (DSMB). The committee will consist of experienced researchers in the Department of Medicine and The Dartmouth Institute at the Geisel School of Medicine at Dartmouth. Such members will consist of researchers who are not involved in the development or execution of this proposal. Per institutional policies, no investigators will have any conflict of interests with or financial stakes in the research outcome. This independent board will follow the policy for data and safety monitoring published by NIH and be responsible for reviewing the following information: adverse consequences (whether serious or minor) to any subject and actions taken to remedy the problem; data quality, completeness, timeliness; performance of the study site; reviewing the entire IRB-approved study protocol, manual of procedures with regard to safety, recruitment, intervention, data management, quality control, analysis and informed consent documents with regard to applicability and readability; recruitment and retention; adherence to protocol; maintenance of confidentiality; external factors impacting safety or ethics of the study; and new or evolving information regarding the expected efficacy and/or safety of the MOWI intervention. Additionally, the DSMB will review the study in relation to intervention effects, gender and minority exclusion; propose appropriate analyses and periodically review developing data on safety and endpoints; consider the rationale semi-annually for continuing the study; review and make recommendations on proposed protocol changes during the trial. All recommended changes to the protocol will be adhered to by the PI. The board will identify relevant data parameters and the format of how the information will be regularly reported. Written reports of each meeting will be sent to the program officer and additional reports as needed, in addition to providing timely advice on issues regarding data discrepancies. They will review manuscripts of trial results. In addition, they will recommend subject recruitment be initiated after receipt of a satisfactory protocol and/or postpone recommendations for initiation of subject recruitment until after the receipt of satisfactory revised protocols. Summary reports of the meetings will be sent to the CPHS at the time of annual reviews. The monitoring committee will ensure safe and effective conduct of the intervention and recommend conclusion of the intervention when significant benefits or risks have developed or the intervention is unlikely to be concluded successfully. All monitoring will be timely and effective. Data from the Research Assistant and Biostatistician will be forwarded to the DSMB for review (and to the Program Officer upon request). The DSMB will conduct reviews of the study every 6 months.

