
All information will be kept confidential during all phases of the intervention, including monitoring, preparation of interim results, review and response to monitoring recommendations. Monitoring will also consider external study factors when interpreting data, including scientific or therapeutic developments that can impact participants. The results of the trial will be forwarded upon publication of its results to all subjects at the conclusion of the intervention. The team will also provide the subject’s healthcare providers with appropriate information, as needed, concerning the individual.

Adverse Event Reporting

Serious, unexpected adverse events (SAE) related to study participation are anticipated to be rare. Study personnel will be trained to report all adverse events. In addition, screening for adverse events potentially related to the study intervention will occur during the routine administration of study assessment measures. These interview-based indicators will augment required SAE reports by study personnel, including specific items in the assessment interviews evaluating episodes of muscle or fall-related injuries, unexpected medical events, medical emergency room admissions, medical hospitalizations, or unplanned medical clinic

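### The structured adverse-event questions are tied to study assessments, and no adverse-event contact is set for people who stop, so harms among non-completers may be under-recorded.

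*Combined protocol and SAP*

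**What the plan says.** Harms reach the study team by several routes.

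- **Staff reports.** Under Adverse Event Reporting, "Study personnel will be trained to report all adverse events".
- **Assessment interviews.** The same section continues with a sentence whose opening words mark it as an addition to those reports: "screening for adverse events potentially related to the study intervention will occur during the routine administration of study assessment measures". The items cover muscle injuries and injuries from falls, unexpected medical events, emergency-room use, hospital stays and unplanned clinic visits. Their role is supplementary: "These interview-based indicators will augment required SAE reports by study personnel".
- **Physician at sessions.** The Data and Safety Monitoring Plan states: "A physician will be available on the premises during all intervention sessions and monitor patient progress and/or adverse events during each session".
- **Monthly review.** The same plan has the research assistant and principal investigator go over withdrawals, data loss, and serious and minor harms each month.

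On attrition, the Retention section says: "We recognize that attrition rates in obesity studies range between 25-50" per cent. For Aim 3 it gives a target of 40 and expects to recruit 53.

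On payment, Recruitment and Retention Strategies offers $100 in Aim 2 "for completing >80% of the visits and assessments for the three-month program (Aim 2"), followed by a mention of $25 per assessment. Aim 3 offers $200 on the same kind of threshold, with no partial payment stated. "Payment will be made at study conclusion according to institutional policies".

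**The concern.** A participant who no longer attends assessments is no longer asked the structured questions. The document describes no call at withdrawal, no adverse-event query after stopping, and no follow-up period for people who leave early. The monthly review looks at withdrawals, but nothing says that the person who withdrew is contacted.

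A participant may stop because of a harm, or have one soon after stopping, so non-completers are a group in which complete recording matters. The Data and Safety Monitoring Plan already expects a low risk of adverse events, and the Overview says the results will support a later randomized trial of home delivery. If harms are sought less thoroughly in people who stop, the data safety monitoring board and the planners of that trial could see a more favourable safety picture than the true one.

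**Working it through.** **1. How many people are concerned.** Inputs, all from Retention: Aim 3 target 40, recruitment 53, attrition range 25–50% cited for obesity studies.

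- Reproducing the recruitment figure: 40 / (1 − 0.25) = 53.3. The stated 53 matches this to within rounding, at the low end of the cited range.
- Implied non-completers: 53 − 40 = 13, and 13 / 53 = 24.5%.

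Aim 2 gives no usable count, because the text has 14 recruited in order to end with 16.

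**2. What each channel offers a person who has stopped.**

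| Channel | Section | What it depends on |
|---|---|---|
| Structured questions | Adverse Event Reporting | An assessment being administered |
| Session physician | Data and Safety Monitoring Plan | Attendance at a session |
| Staff reports | Adverse Event Reporting | Staff learning of the event |
| Monthly review | Data and Safety Monitoring Plan | The event already being known |

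Reporting deadlines for serious events and deaths run from the time the study learns of them, so an unknown event starts no clock. The described exchange with primary care goes outward: providers are kept informed, and no return route is set. Part of the programme is delivered at home, and the text does not explain how a physician is on the premises there.

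**3. Whether the size can be stated.** It cannot. Let k be the event risk in non-completers relative to completers, and c the share of non-completers' events that the other channels pick up. With 40 completers fully recorded and 13 non-completers,

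share of all events recorded = (40 + 13kc) / (40 + 13k).

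Neither k nor c is in the document. With assumed values:

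| | k = 1 | k = 2 | k = 4 |
|---|---|---|---|
| c = 0 | 40/53 = 75% | 40/66 = 61% | 40/92 = 43% |
| c = 0.5 | 46.5/53 = 88% | 53/66 = 80% | 66/92 = 72% |
| c = 1 | 100% | 100% | 100% |

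The c = 0 row is a floor and is not expected, since the other channels will catch some events. The table shows only that the answer turns on c, which the plan leaves open.

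**The case against.** The strongest reply is that adverse-event capture is not confined to assessments. This is right. A reader who sees the assessment sentence alone might infer that events are sought nowhere else. The sentence before it, its opening words and the physician's duty at sessions rule that out. A harm at a session that makes someone stop falls within the physician's and staff's remit.

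A reader might also infer from the payment rule that people who are harmed forfeit their money, avoid assessments and so are the group least likely to have the harm recorded. The document does not support that:

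- A threshold without partial payment is the plain reading for Aim 3 only. Aim 2 is ambiguous, and Aims 1a, 1b and 4 have no such threshold.
- The rule tolerates some missed visits, and no visit count is given.
- Assessments count toward the threshold, so someone near it has a reason to attend the interview.
- Payment does not depend on being free of events.

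It can also be said that withdrawal procedures may stand elsewhere. The text refers to a Human Subjects section, an appendix and a manual of procedures, none of which is in this document, and the consent pages were not available here. This limits the point to what the document sets out.

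What remains is that none of the described channels actively seeks harms from a person who has stopped.

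**Conclusion.** The point holds as a gap in ascertainment. It is not an error in a figure. Structured questioning follows the assessment schedule, the other channels rely on attendance or on staff hearing of the event, and no adverse-event contact is described for people who stop. In Aim 3 this concerns about 13 of 53 participants (24.5%), taking the difference between recruitment and target as the planned number of non-completers.

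The effect on adverse-event rates is unknown. Any statement that the recorded rate would be too low by a given factor needs assumed event rates and an assumed level of capture among people who stop, and the document gives neither. If the other channels catch every such event, there is no loss.

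The >80% payment condition is not shown to be a fault. It is one of the incentives the plan chose to limit drop-out, and removing it would be a trade-off. Only the Aim 2 wording needs clarifying. Overall this is a cheap, worthwhile improvement.

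**What to change.** In Adverse Event Reporting, add three things:

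1. For anyone who stops sessions or misses an assessment, the research assistant asks the existing adverse-event items by phone at that time, and again at that person's planned final assessment date.
2. The reason for stopping is recorded.
3. Adverse events are reported with all who started as the denominator, split into completers and non-completers.

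The cost is a wording change plus two short calls per non-completer, about 13 × 2 = 26 calls in Aim 3 at the planned attrition. Reminder phone calls are already part of the plan, so no new staff role is needed.

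Separately, in Recruitment and Retention Strategies, state whether the $25 per assessment in Aim 2 is paid to someone below the 80% threshold or merely itemises the $100. This costs one sentence.
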